Second experimental session day: During the second experimental session day, participants will be lying down in a supine position within an MRI scanner during administrations of placebo (inhaled air) and a 15 or 12 µg/kg dose of salvinorin A (whichever dose did not yield erratic movement during the first experimental session). Participants will be told that they are being continuously monitored by an intercom and can stop the scan at any time, but that it is best for them to remain still and refrain from any head, face or jaw movements. Participants will also be told that a study team member will remain in the scanner room with them throughout the procedures. The placebo condition (inhaled air) will always precede the salvinorin A condition. MRI scans will be used to obtain structural brain images, as well as functional data that permit the direct measurement of oxygenated blood (using blood-oxygenation level dependent [BOLD] techniques) to assess acute effects of salvinorin A on brain function. Heart rate (via pulse oximetry), respiration, and end-tidal carbon dioxide may also be collected in order to correct for artifacts in BOLD signal. BOLD signal data will be collected during two 20 minute scans (one scan for placebo and one scan for salvinorin A). During each scan, an inhalation period will begin 30 seconds after the beginning of BOLD data collection, and will be cued via audio stimulus using MR-safe headphones. A study team member will be present in the scanner room with the volunteer during scanning and inhalation procedures, to provide support to the participant during procedures. Participants will be told that one of the inhalations will be the dose of salvinorin A that they received during the first session, and the other inhalation will be either a placebo or a variable dose of salvinorin A, but no dose of salvinorin A higher than the dose they received during the first session will be administered.

All imaging procedures will be performed using 3T Siemens MRI scanner at the MRI Research Service Center at Johns Hopkins Hospital, by individuals specifically trained in these procedures. MRI assessments

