involve standard methods and established pulse sequences utilized in research evaluations and do not involve the injection of any contrast or other invasive procedures. We will work closely with the neuroimaging experts in the MRI Research Service Center to ensure safe and effective implementation of the tasks conducted in the scanner. [name], the principle investigator on the team, has extensive experience with brain imaging and is currently leading MRI and PET neuroimaging studies of the acute effects of the classic hallucinogen psilocybin. [name] will oversee the development and conduct of brain imaging procedures and analysis of the resulting data.

After completing the scanning procedures, the participant will complete brief (e.g., 10-15 minute) behavioral measures and/or questionnaires regarding the subjective effects that they experienced during the scanning session. These measures will be used along with ratings made in the scanner to interpret differences in brain activation between participants and across conditions. For example, changes in brain activation may be correlated with ratings of subjective effects (e.g. the Mystical Experience Questionnaire, or the Challenging Experience Questionnaire) experienced during the scanning procedures. Subjects will also be asked to write a narrative description of the experience of each salvinorin A session within about one week after a session.

Participants will undergo drug administration during collection of BOLD signal in the MRI. Real-time fMRI analysis techniques may be employed to monitor volunteer head motion as the scans are collected. If participants exhibit gross (> 1mm of movement in any plane) frequent (for more than 25% of the scan time) head motion, we may repeat the given drug administration and scan, since frequent gross motion may invalidate BOLD imaging data (Power, Barnes, Snyder, Schlaggar, & Petersen, 2012; Power et al., 2014). We may repeat drug administration and scanning up to two times. No more than one salvinorin A administration will occur on a single day. Repeated administrations of salvinorin A may occur on consecutive days.

Schedule of Events for Second Experimental Session Day

Time Point (minutes from drug administration)	Procedure	Description
-65 (or more)	Intake procedures	Participant will complete drug and pregnancy urine tests, and complete a pre-session questionnaire to assess the psychological “set” of the volunteer (including mood state and cognitive state)

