Inhalation device: The inhalation delivery system (i.e. pipe) is made of glass. The part of the glass pipe which will hold the salvinorin A will be a 5 ml round bottom chemistry flask meeting American Society for Testing and Materials (ASTM) specification E438 for Type I, Class A borosilicate glass. The non-ferromagnetic tubing attached to the inhalation delivery system will be polytetrafluoroethylene (PFTE) tubing, which meets FDA standard for food contact, has a high maximum working temperature (260° C, which is higher than the 244-245° C vaporization point of salvinorin A), and does not thermally degrade until temperatures greater than 400° C. The tubing will be 0.635 cm inner diameter, and up to 400 cm in length. The same tubing will be used for a given subject or a set of new tubing will be used between drug administrations. Tubing will not be cleaned with solvents.

A label will be prepared for each test dose and affixed to the neck of the 5mL round bottom flask containing the dose. This label will be removed immediately prior to heating the flask for drug administration. Each dose will be labeled with subject name, date, session number, pharmacy compounding number, dose of salvinorin A, and a statement that the drug is limited to investigational use only.

Study Statistics

Primary outcome variable: The primary outcome measures for this study will consist of changes in activity and connectivity of brain regions during the acute effects of salvinorin A, compared to the preceding period after inhalation of the placebo condition (inhaled air).

Secondary outcome measures: The secondary outcome measures will include a range of subjective measures described below.

Subject-rated overall drug strength: Volunteers will be prompted to verbally rate the overall drug strength on an 11-point scale (0 – none, no effect to 10 – extreme, strongest imaginable) at various

time points (e.g., 1, 2, 3, 4, 5, 10, 15, 20, 25, 30, and 45 minutes after each drug inhalation) during the first experimental drug session day.

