Using the lower (more conservative) of the two effect sizes from our previous psilocybin and salvinorin A studies ($d = 0.89$), and an alpha of 0.05, 6 volunteers would be sufficient to detect effects on ratings of drug intensity with 95% power. Empirical and simulation studies have provided recommendations for sample size of imaging experiments (Zandbelt et al., 2008). For similar parameters, including an effect size of 0.89, alpha of 0.05, and 80% power, 21 participants are necessary to power an ROI-based analysis of effects on brain activity similar to behavioral effects of psilocybin. Far fewer participants would be necessary to detect effects similar to the behavioral effects of salvinorin A, though no specific sample size recommendations were made by Zandbelt and colleagues for such a large effect size ($\eta^2 = 0.81$, equivalent to $d > 4$). Thus, the proposed study of 20 participants would be powered to detect clinically significant differences in brain activity between placebo and salvinorin A conditions. Given that consent will be obtained at the initial in-person screening interview, we are requesting approval to consent up to a total of 200 volunteers.

MRI data analyses: MRI data will be preprocessed using standard methods. The time course of brain regions in standard brain atlases (e.g. Chen Atlas or Power Atlas) will be extracted and submitted to functional connectivity analysis.

Statistical analysis of behavioral data: Baseline demographic data will be summarized with descriptive statistics to describe the volunteer population. For measures assessed at multiple time-points, including subjective effects ratings, both time-course and peak-effect data will be examined. For outcomes assessed at screening and one week after the final salvinorin A session, a paired t-test will be used to assess change from baseline (screening). Behavioral measures (including monitor ratings, subjective effects ratings, and questionnaire data) will be correlated with brain-imaging outcome measures to investigate the relationship between individual differences in subjective drug response and individual differences in neural drug response.

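### Activity is half of the primary outcome and the only imaging quantity with a power claim, but only connectivity has a planned analysis, and 30 seconds of pre-inhalation BOLD would identify a level change weakly

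*Combined protocol and SAP*

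**What the plan says.** Study Statistics, Primary outcome variable, defines the primary outcome as "changes in activity and connectivity of brain regions during the acute effects of salvinorin A". The reference is the placebo run that comes before, since these changes are "compared to the preceding period after inhalation of the placebo condition (inhaled air". The opening statement of objectives has the same two parts.

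Statistical analysis plan, MRI data analyses, consists of standard but unspecified preprocessing, after which time courses from atlas regions "will be extracted and submitted to functional connectivity analysis". No activity measure, contrast, baseline, drift model, region list or test is given. The section on the second experimental session day says that "changes in brain activation may be correlated with ratings of subjective effects", but does not say how activation would be derived.

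Statistical analysis plan, Sample size, gives 21 as the number needed for a region-of-interest analysis of brain activity at d = 0.89, alpha 0.05 and 80% power. It concludes that 20 participants leave the study "powered to detect clinically significant differences in brain activity between placebo and salvinorin A conditions". The same section notes that the effect size is behavioural and does not come from imaging.

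On acquisition, the section on the second experimental session day describes one 20-minute BOLD run for placebo and another for drug. In each, "an inhalation period will begin 30 seconds after the beginning of BOLD data collection". On order: "The placebo condition (inhaled air) will always precede the salvinorin A condition". Recording of heart rate, respiration and end-tidal carbon dioxide is optional. The Administration method text gives 45 seconds as an example of the inhalation and hold time.

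**The concern.** Outcome, analysis and power do not line up. The quantity with a power statement has no analysis, and the quantity with an analysis has no power statement. If an activity result is reported, its measure and contrast will have been chosen after the data were available. If none is reported, half of the primary outcome goes unanswered and the power statement refers to nothing.

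The run structure adds to this. BOLD signal has no absolute scale that carries from one run to the next, so raw means of the drug and placebo runs are not directly comparable. A change in mean level needs a reference inside each run. Here that reference is the first 30 seconds, and the next event, inhalation with a breath hold, can itself move the BOLD signal. The end of the run is no safe substitute: the protocol says only that subjective effects resolved within 45 minutes, and the run lasts 20. Subtracting placebo removes only what the two runs share, and the order is fixed.

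**Working it through.** **1. Outcome, analysis and power side by side.**

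| | Activity | Connectivity |
|---|---|---|
| Primary outcome | named | named |
| MRI analysis | none | atlas time courses, functional connectivity |
| Power statement | 21 for 80% power; 20 planned | none |

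**2. The plan's figure of 21.** At d = 0.89, two-sided alpha 0.05 and 80% power (noncentral t), a paired t-test needs 12 participants, taking d as standardised by the SD of the differences. A two-sample t-test needs 21 per group (power 80.3%). With 20 participants, paired power is 96.5%. So 21 coincides with an independent-groups calculation. The plan takes it from a cited imaging sample-size study whose settings are not reproduced, so its origin cannot be confirmed. Neither calculation says anything about connectivity, and neither decides whether activity can be estimated.

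**3. Share of the run before inhalation.** 30 s / 1,200 s = 2.5%. A 5-minute lead-in in the same run would be 300 / 1,200 = 25%.

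**4. Precision of a level change within one run.** The documents give no repetition time, noise model or effect shape. Assumptions: 1 to 2 s per volume; first-order autocorrelation of 0 to 0.5; a sustained step; and 60 s from the inhalation cue left out (the 45 s example plus a margin). The unit is the noise SD of one volume.

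With a constant baseline and independent noise, SE = √(1/n_pre + 1/n_post). At 1 s per volume:

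- 30 s lead-in: √(1/30 + 1/1,110) = 0.185
- 300 s lead-in: √(1/300 + 1/840) = 0.067
- ratio: 0.185 / 0.067 = about 2.75

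At 2 s per volume the values are 0.262 and 0.095, with the same ratio.

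The other drift models were fitted by generalised least squares, with the run length held at 1,200 s. The ranges cover the assumptions above.

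| Drift model | SE, 30 s lead-in | SE, 300 s lead-in | Ratio |
|---|---|---|---|
| Constant | 0.19–0.43 | 0.07–0.16 | 2.60–2.75 |
| Linear | 0.19–0.45 | 0.11–0.27 | 1.67–1.76 |
| Quadratic | 0.22–0.51 | 0.17–0.41 | 1.23–1.27 |
| 128 s high-pass | 2.25–4.75 | 1.40–3.13 | 1.52–1.61 |

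A drug-minus-placebo change multiplies each SE by √2 = 1.41.

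**5. Role of the filter.** With a 128 s high-pass and the inhalation period left out, the SE exceeds one noise SD for either lead-in: the filter absorbs most of a sustained change. If the inhalation period is kept in, the high-pass SE is smaller (0.36–0.72 with the 30 s lead-in), but the estimate then leans on the seconds around the cue, and the longer lead-in brings no gain (ratio 0.91–0.94). A longer lead-in therefore helps only with a drift model that spares a sustained change, and the plan states no drift model.

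**The case against.** A reader might infer that activity cannot be estimated at all from these runs. The documents do not support that, for three reasons.

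- The standard errors above are finite. In the best case of the 30 s design, the drug-minus-placebo SE is 0.185 × 1.41 = 0.26 noise SD per person. Averaged over 20 people it is 0.26 / √20 = 0.06, before any variation between people. That is imprecise for an individual but not hopeless for a group.
- The stated comparator is the placebo period, not the 30 s segment. The placebo run has the same length, lead-in and cued inhalation, so effects common to both runs cancel.
- The plan never says that activity means mean BOLD level. The amplitude of signal fluctuation, or a regression on the time course of drug-strength ratings from the first session, needs no pre-drug baseline.

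All three stand, and they limit the point to weak identification of one natural reading of activity. They do not repair the mismatch, because none of these measures is specified. Cancellation is also partial: drift or physiological change that differs between a first and a second run remains, and the recordings that could correct for it are optional.

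It is also fair to object that starting inhalation 30 s into the run is an acquisition choice and not an error in itself. That is correct; it matters because of what the outcome and the power statement promise.

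**Conclusion.** The point holds as a mismatch between the primary outcome, the MRI analysis and the power statement. This part rests on the documents alone. The claim of power for brain activity has no analysis behind it, and connectivity has no power statement.

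The acquisition part is one of degree. With 2.5% of each run before inhalation, a sustained mean-level change is weakly identified and confounded with drift. Its SE is about 1.25 to 2.75 times what a 5-minute lead-in would give at the same run length. That range rests on the assumed repetition time, noise model, step shape and 60 s exclusion. It does not justify saying that the trial cannot address activity.

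**What to change.** Choose one.

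**(a) Keep activity.** Start BOLD several minutes (for example 5) before the inhalation cue in both runs. Define activity as the within-run change from that baseline, drug minus placebo, leaving out the inhalation and hold period. Name the regions and the test, and state a drift model that does not filter out a sustained change. Cost: about 5 more minutes per run (4.5 if the current 30 s counts towards the 5). If run length is fixed, it costs 4.5 of the 19.5 post-inhalation minutes (4.5 / 19.5 = 23%), a loss that the connectivity analysis shares. This option is open only for scans not yet acquired.

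**(b) Drop activity.** Restrict the primary outcome to connectivity and withdraw the claim of power for brain activity. The power sentence cannot simply be reworded for connectivity: d = 0.89 is a behavioural effect size, and the figure of 21 is for region-of-interest activity. State instead that power for connectivity was not calculated. Cost: wording, and a narrower stated claim.

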-40 (approximate)	Setup	The participant will be brought to the MRI suite. The prepared salvinorin A dose for this participant and session will be brought from the BPRU pharmacy to the MRI suite. All materials and equipment for drug delivery and study monitoring will be set up, including passing the non-ferromagnetic inhalation tube through the pass-through panel from the MRI control room to the MRI scanning room. The volunteer will be placed in a head-first supine position on the scanner bed, with the head placed within the MRI head coil. The volunteer will be provided with MR-safe earbud head phones that provide hearing protection, as well as additional padding to prevent head movement and further provide hearing attenuation, consistent with standard MRI procedures. The inhalation tubing will be taped on to the MRI head coil in a position that is accessible to the volunteer, and the volunteer will be moved into the magnet. A study team member will remain with the volunteer in the MRI scanning room throughout the procedures. Structural scanning procedures will then commence.
-20	Placebo scan	A 20-minute EPI scanning sequence will be started, and placebo inhalation will begin 30 seconds after the start of the EPI scan. The participant will be instructed via inserted MR-safe earbud headphones to begin the inhalation procedure.
0	Salvinorin A scan	After verbally confirming that the volunteer is comfortable and ready to continue, a 20-minute EPI scanning sequence will be started, and salvinorin A inhalation will begin 30 seconds after the start of the EPI

		scan. The participant will be instructed via inserted MR-safe earbud headphones to begin the inhalation procedure.
20	Scan end	After the salvinorin A scan has completed, the volunteer will be removed from the MRI and brought to a private adjacent room and verbally debriefed.
25	Final Questionnaires	The participant will be asked to complete brief (10-15 minute) behavioral measures and/or questionnaires regarding the subjective effects that they experienced while in the scanner.

The schedule of events for the second experimental session day is approximate, but the listed events will always occur in the same sequence.

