After each experimental session, volunteers may have a follow-up telephone conversation or in-person meeting (up to 8 hours) with study staff to discuss the session and any thoughts and feelings that emerged from the experience. These follow-up conversations may also coincide with subsequent experimental session days (before drug administration). The general purpose of the meetings following sessions is to provide a context for discussing and interpreting experiences from the drug administration sessions. Volunteers will also complete follow-up questionnaires and a telephone call with study staff one week after the final drug administration session. Study staff contact and follow-up questionnaires will assess whether there are lasting psychological effects of salvinorin A.

Study duration and number of study visits required of research participants: Participants are expected to complete between 2 and 6 study visits. This will, at minimum, include 1 screening visit, a preparation meeting with the guides to review session procedures and establish rapport, and 2 drug administration sessions (approximately 2 to 3 hours each). The preparation meeting may coincide with the screening visit, or with the first experimental drug administration session. The first and second drug administration sessions may also occur on the same day. Also, as described above, we may repeat any drug administration up to two times if there was an experimental issue rendering the session invalid, and we may lower the dose of salvinorin A from 15 to 12 $\mu\text{g}/\text{kg}$ if a given volunteer exhibited erratic or involuntary movements or reported no memory for the experience. Also, we may schedule additional pre-and post-session meetings if study staff judge that rapport and psychological stability has not been sufficiently well established to proceed, or if there is a need for discussion and interpretation of experiences from the drug administration sessions. The total study duration for each volunteer will be between 1 and 6 weeks. Each volunteer's total

study duration will be dependent upon schedules and availability of the volunteer as well as the experimental resources of the BPRU and MRI Research Service Center.

Schedule of Study Visits

Visit	Purpose	Description
	Phone Screening	An initial phone screening will determine whether an individual meets major inclusion/exclusion criteria, and thus whether they are eligible for in-person screening.

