Visit 1	In-Person Screening	This evaluation includes a history and physical examination, structured psychiatric diagnostic interview, urine drug test, and, for females, a urine pregnancy test. A blood sample (15 ml) will be drawn for medical screening.
Visit 2	Preparation Meeting	The purpose of this meeting is to develop rapport and trust between the participant and study staff, which is understood to minimize the risk of fear or anxiety reactions during sessions with salvinorin A. The purpose of this meeting is also to prepare the volunteer for experiences they may have under the effects of salvinorin A.
Visit 3	First Experimental Session Day	Participants will be administered salvinorin A via inhalation while lying down. Volunteers will complete several assessments approximately 45 minutes after drug administration.
	Follow-up conversation (optional)	After the first experimental session day, volunteers may have a follow-up telephone conversation or in-person meeting (up to 8 hours) with study staff to discuss the session and any thoughts and feelings that emerged from the experience. This conversation after the first drug administration day may also coincide with the second experimental session day (before drug administration). The general purpose of follow-up conversations is to provide a context for discussing and interpreting experiences from the drug administration sessions.
Visit 4	Second Experimental Session Day	Participants will be lying down in a supine position within an MRI scanner during administration of placebo (inhaled air) and a 15 µg/kg dose of salvinorin A.
	Follow-up conversation (optional)	After the second experimental session day, volunteers may have a follow-up telephone conversation or in-person meeting (up to 8 hours) with study staff to discuss the session and any thoughts and feelings that emerged from the experience. The general purpose of this meeting is to provide a context for discussing and interpreting experiences from the drug administration sessions.
1 week after Visit 4	Final follow-up	One week after the final experimental session day, volunteers will have a telephone conversation with study staff to discuss any lasting psychological effects of salvinorin A, and they will complete online questionnaires.

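### On the scan day a verbal debrief of unspecified content is fixed before the subjective-effect questionnaires that may be correlated with brain activation

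*Combined protocol and SAP*

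**What the plan says.** The Schedule of Events for Second Experimental Session Day has two consecutive rows after the salvinorin A scan. At +20 minutes (Scan end), "the volunteer will be removed from the MRI and brought to a private adjacent room and verbally debriefed". At +25 minutes (Final Questionnaires), the participant completes brief "behavioral measures and/or questionnaires regarding the subjective effects that they experienced while in the scanner", which take 10 to 15 minutes. The note under the table treats the clock times as approximate but the order as binding: "the listed events will always occur in the same sequence".

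The text on the second experimental session day says how these measures will be used. Together with ratings made in the scanner, they help interpret differences in brain activation, and "changes in brain activation may be correlated with ratings of subjective effects", with the Mystical Experience Questionnaire and the Challenging Experience Questionnaire as examples. The protocol's opening section makes the relation between individual subjective effects and individual brain response a secondary objective. The paragraph on statistical analysis of behavioral data plans correlations of monitor ratings, subjective-effect ratings and questionnaire data with the imaging outcomes.

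**The concern.** A retrospective self-report is best taken before anyone discusses the experience with the respondent. Here the order is reversed by rule, in every scan session. The protocol does not say what the debrief covers, who conducts it, or what must be left out of it. Its content may therefore differ between volunteers, and nothing in the plan records it.

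What is at stake is the subjective side of the secondary objective. If the conversation alters scores by amounts that vary between volunteers and are unrelated to neural response, the brain-behaviour correlations are weakened. If the alteration is related to neural response, for example because a strong reaction prompts a longer talk, the correlations could move either way. The analysis cannot separate this out afterwards, because every volunteer is debriefed first and no variable describes the debrief.

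**Working it through.** **Order of events.** This is a matter of reading, not calculation.

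- Scan end and debrief: nominal +20 minutes. Questionnaires: nominal +25 minutes. The gap is 25 − 20 = 5 minutes, which must hold removal from the scanner, the move to another room and the debrief.
- The questionnaires then run to about 25 + 10 = +35 or 25 + 15 = +40 minutes.
- The text on the second experimental session day places the questionnaires after scanning and does not mention the debrief, so it does not conflict with the table. Nowhere do the documents put the scan-day questionnaires before the debrief.

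**Which scores are affected.** The text on the second experimental session day refers to ratings made in the scanner, which would precede the debrief, but the scan-day table schedules none. The Study Statistics section places the timed drug-strength ratings and the tremor scale on the first session day. The questionnaires are therefore the only scan-day self-reports with a scheduled time, and they come after the debrief. They are not the only measures that may enter the correlations.

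**Illustrative size.** The plan gives no figure to reproduce. Every input here except the sample size is an assumption.

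- n = 20, the planned number of completers.
- Assumed true correlation between score and brain measure: 0.50.
- Assumed added variance, unrelated to neural response, as a fraction v of the score variance: 0.10, 0.25 or 0.50.
- Attenuated correlation = 0.50 / √(1 + v).
- Power of the two-sided 0.05 correlation t-test, by simulation with 200,000 replicates of bivariate normal data.

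| v | Formula | Correlation | Power at n = 20 |
|---|---|---|---|
| 0 | 0.50 / √1.00 | 0.50 | 64% |
| 0.10 | 0.50 / √1.10 | 0.48 | 59% |
| 0.25 | 0.50 / √1.25 | 0.45 | 53% |
| 0.50 | 0.50 / √1.50 | 0.41 | 45% |

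The table shows what a given amount of noise would do. It is not evidence that the debrief produces that amount. A constant shift c in every score gives corr(score + c, brain) = corr(score, brain), so a uniform effect costs this analysis nothing.

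**The case against.** The strongest reply is that the debrief may be harmless. Only about five nominal minutes are available, part of them spent leaving the scanner and changing rooms. A short well-being check fits the text as well as a substantive talk does. Half the score variance from so brief an exchange is hard to believe, and at 10% the loss is small. This stands: it limits the size of the point. It does not answer it, because the protocol neither limits the debrief to a check nor says what it may cover.

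Four stronger readings are tempting, and the documents do not support them.

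- A reader might infer that the debrief is an interpretive discussion, because the section on meetings with study staff says post-session meetings "provide a context for discussing and interpreting experiences from the drug administration sessions". That describes separate follow-up conversations, which the Schedule of Study Visits marks as optional. It does not define the debrief. That staff conduct the debrief and that it covers the experience are reasonable inferences, but neither is stated.
- A reader might infer that volunteers learn at the debrief which inhalation was air. Air always comes first, so staff who follow the protocol know the order, but nothing says that it is disclosed. Volunteers have also already met the active drug in the first session, and many might recognise air unaided.
- A reader might see the same fault at one week, because the Final follow-up row says "volunteers will have a telephone conversation with study staff to discuss any lasting psychological effects of salvinorin A, and they will complete online questionnaires". The section on meetings with study staff and the illustrative timeline both name the questionnaires first, and the fixed-order notes apply only to the two session-day tables. No order is set at one week.
- A reader might object that no debrief is listed before the first session's questionnaires. Those also follow repeated staff contact, setting and timing differ in any case, and no comparison of questionnaire scores between sessions is planned.

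**Conclusion.** The concern holds in a limited form. In every scan session the protocol puts a debrief with no defined content before the subjective-effect questionnaires, and those scores may be correlated with brain activation. This is an avoidable route for noise or a shift to enter the scores. Its size and direction are unknown.

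It would go too far to say that all scores in the brain-behaviour correlations are collected after the debrief: in-scanner, monitor and first-session ratings may enter too. The questionnaire correlations are themselves given as something that may be done, with the two instruments as examples. The primary comparison of brain activity and connectivity between salvinorin A and placebo does not depend on these scores. This is a minor, inexpensive improvement to a secondary objective. It rests on the assumption that the debrief may touch on the experience; if it was only ever a well-being check, a sentence saying so would settle the matter.

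**What to change.** In the Schedule of Events for Second Experimental Session Day, take the debrief out of the Scan end row and place it after the Final Questionnaires row. Between scan end and the questionnaires, keep only a brief well-being check that does not discuss the content of the experience or what was inhaled. Because the note under the table already makes the order binding, no other text is needed to enforce it.

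The cost is that discussion of the experience starts about 10 to 15 minutes later, the time the questionnaires take. No extra visit, staff or assessment is required.
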